7.3 LOST TO FOLLOW-UP

All participants will be considered lost to follow-up if they fail to return for any one of the scheduled visits outlined in Section 1.3 and is unable to be contacted by the study site staff.

The following actions must be taken if a participant fails to return to the clinic for a required study visit:

- The site will attempt to contact the participant and reschedule the missed visit within the next 7 days and counsel the participant on the importance of maintaining the assigned visit schedule and ascertain if the participant wishes to and/or should continue in the study.
- Before a participant is deemed lost to follow-up, the Principal Investigator or designee will make every effort to regain contact with the participant (where possible, 3 telephone calls and, if necessary, a certified letter to the participant's last known mailing address or local equivalent methods). These contact attempts should be documented in the participant's medical record or study file.

• Should the participant continue to be unreachable, they will be considered to have withdrawn from the study with a primary reason of lost to follow-up.

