To compare the range of motion provided by the SB to the DB, and to verify that the DB consistently maintains proper foot position and leg alignment during use, parents will be given the option of consenting to video recordings being taken during the hospital visit of the patient's feet and legs while wearing their prescribed bar. This recording will occur on Day 30 of the study period by a member of the study team. These videos will be closely studied to compare the range of motion provided by the SB to the DB, and to verify that the DB consistently maintains proper foot position and leg alignment during use. Note that audio will be removed from the videos.

Patient recruitment will be documented in an electronic enrollment log. To evaluate ease of recruitment, this enrollment log will also include patients who do not wish to participate in the study and their reason(s) for refusal. The enrollment log will also record information on patients that do not adequately fit the available prototype but are otherwise eligible, including patient age and fit issues. This will serve to inform future adaptations of the new DB.

During the intervention period, all patients will be monitored for brace fit by the PI and/or physiotherapist [name]. A blinded outcomes assessor will clinically evaluate all patients to assess foot shape for possible recurrence or complications. The outcomes assessor will be a skilled clubfoot provider and will not be made aware of which bar was provided to the patient and is

independent of the design team. Once the trial is complete, the patient's care will resume with their primary clubfoot provider.

Clubfoot patients are normally reviewed in clinic every 3-6 months. If scheduling permits, Day 0 of the study period will align with patient's already scheduled follow up visit. All patients will therefore require either 3 or 4 extra visits (possibly on Day 0, and surely on Day 7, Day 30, and Day 90). These extra visits will consist of the same evaluations done in the routine clubfoot monitoring protocol, in addition to the study-related questionnaire, brace wear log, video recording (on Day 30 only), and temperature sensor data collection.

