Three surveys will be administered to parents on Day 0, Day 30, and Day 90 of the study period. These surveys will be collected and managed using REDCap (Research Electronic Data Capture) hosted at SickKids. Parents will also be asked to complete a brace wear log to be submitted at Day 30 and Day 90 of the study period.

Most patient information that will be reviewed in this study is data being collected and stored per the REB-approved Clubfoot Research Registry protocol (REB #1000053919). All patients enrolled in study this will also be enrolled in Clubfoot Research Registry, if not already enrolled.

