5 STUDY POPULATION

5.1 INCLUSION CRITERIA

In order to be eligible to participate in this study, an individual must meet all of the following criteria:

- 1. Ability of parent/care giver to complete brace wear log/surveys in English
- 2. Diagnosis of idiopathic clubfoot (unilateral or bilateral).
- 3. Current use of a SB with their Foot Abduction Brace.
- 4. In the minimum 12-hour per day bracing stage of the Ponseti treatment
- 5. Aged 1 to 3 years (as the DB prototype was designed based on the average size and strength of a child within that age group).
- 6. Well-corrected clubfoot/clubfeet (Pirani score ≤ 0.5)
- 7. Enrollment in the SickKids Clubfoot Research Registry.

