7.2 PARTICIPANT DISCONTINUATION/ WITHDRAWAL FROM THE STUDY

Participants are free to withdraw from participation in the study at any time upon request. An Investigator may discontinue or withdraw a participant from the study for the following reasons:

- Withdrawal of informed consent (participant or parent/guardian withdraw for any reason)
- If any clinical Adverse Event (AE), laboratory abnormality, or other medical condition or situation occurs such that continued participation in the study would not be in the best interest of the participant.
- If the participant meets an exclusion criterion (either newly developed or not previously recognized) that precludes further study participation.

The reason for participant discontinuation or withdrawal from the study will be recorded in the study enrollment log. Patients who do not follow the prescribed bracing schedule will still be included in the study and recorded with the intention to treat principle. Similarly, if the DB prototype breaks or malfunctions and cannot be quickly repaired, the patient will return to their original SB but will not be withdrawn from the study.

Participants who sign the informed consent form, but do not return for study visits 1, 2 and/or 3 will be replaced. Participants who sign the informed consent form, and return for study visits 1, 2 and 3 but subsequently withdraw, or are withdrawn or discontinued from the study will not be replaced. The data from participants who are withdrawn or discontinued from the study will be used in the analysis unless the participant requests otherwise.

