9.2 POPULATIONS FOR ANALYSES

The following study populations are defined and will be analyzed as specified below:

- Intent to treat population: the total population of patients registered in the study.
- Experimental arm population: all registered participants in the experimental arm with DB.
- Control arm population: all registered participants in the control arm with SB.

- Safety population: all registered participants who wore their FAB as prescribed for the full 90-day study period.
- Brace discomfort population: all registered participants who have any history of brace intolerance or indicated in the parent-reported survey that they are not comfortable/have concerns with their original FAB.
- Brace comfort population: all registered participants who have no history of brace intolerance and indicated in the parent-reported survey that they are comfortable/have no concerns with their original FAB.

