9.3.3 ANALYSIS OF THE SECONDARY ENDPOINTS

Parent-reported comfort levels will be determined by parent-reported surveys with 5-point Likert scale responses. Results from these surveys will be analyzed with descriptive statistics for the intent to treat population, the brace discomfort population, and the brace comfort population.

Daily bracing times will be measured by a temperature sensor added in each patient's boots for the entire 90-day study period. The number of hours the brace is worn per day will be divided by the standard number of desirable hours in brace (12 hours) in order to obtain a fraction that quantifies the patient's adherence to the FAB. Mean 'adherence fractions' will be calculated for patients in each arm, and then compared using descriptive statistics. This analysis will be performed for the intent to treat population, the brace discomfort population, and the brace comfort population. This data will be compared to the self-reported brace wear hours by parents in their daily logs.

To ensure minimal efficacy of the DB prototype, all signs of clubfoot recurrence will be carefully examined at each study visit. The null hypothesis is that 'the dynamic bar does not lead to higher rates

of clubfoot recurrence,' and it will be rejected if the number of patients in the safety population that develop clubfoot recurrence during the 90-day study period, is substantially greater in the experimental arm than it is in the control arm (i.e. more than 2 instances of clubfoot recurrence in the experimental arm than in the control arm). Note that this endpoint is not intended to prove safety or efficacy, but rather to ensure that the design may prevent early recurrence before a larger-scale trial is conducted. Clubfoot recurrence is defined as a Pirani score > 0.5, a new occurrence of cavus, adduction and/or hindfoot varus, or a loss of passive ankle dorsiflexion (equinus) of < 10 degrees above neutral or a reduction of 5 or more degrees from the previous visit. Note that all clinical tests required to diagnose recurrence are routinely performed as standard clubfoot care.

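### The recurrence count omits children who leave the study: it is taken in 90-day completers, and no outcome is sought after loss or withdrawal, although the Registry could often supply one

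*Combined protocol and SAP*

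**What the plan says.** **Which children are counted.** Section 9.3.3 rejects its null hypothesis of no higher recurrence with the dynamic bar (DB) if recurrences in the DB arm exceed those in the standard-bar (SB) arm by more than two, that is by at least three. It makes this count in the safety population, which Section 9.2 defines as "all registered participants who wore their FAB as prescribed for the full 90-day study period". Comfort and wear time, by contrast, are analysed in the intent-to-treat population among others.

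**What happens when a child leaves.** Section 7.3 provides for rescheduling, telephone calls and a letter. If these fail, "they will be considered to have withdrawn from the study with a primary reason of lost to follow-up". Section 7.2 adds: "The data from participants who are withdrawn or discontinued from the study will be used in the analysis unless the participant requests otherwise". It also says that consented participants who "do not return for study visits 1, 2 and/or 3 will be replaced". Section 8.2.5 records adverse events occurring on study and ends their follow-up when a child is deemed lost. No section provides for a recurrence outcome that arises after loss or withdrawal, and there is no missing-data rule for recurrence.

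**What exists outside the study visits.** Inclusion criterion 7 in Section 5.1 is "Enrollment in the SickKids Clubfoot Research Registry". Section 4.1 says that all participants "will also be enrolled in Clubfoot Research Registry, if not already enrolled". Section 4.1 also states: "Clubfoot patients are normally reviewed in clinic every 3-6 months". Section 9.3.3 states: "Note that all clinical tests required to diagnose recurrence are routinely performed as standard clubfoot care".

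**The concern.** The count loses these children in two ways. First, a child who is lost or withdrawn cannot be shown to have worn the brace as prescribed for 90 days, so the safety population leaves that child out, including any examination already made at Day 7 or Day 30. Second, nothing is collected afterwards. Widening the population without seeking the outcomes leaves gaps. Seeking the outcomes without widening the population leaves the count as it is.

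Families may leave for reasons connected with the brace or the foot, and Section 7.2 lets an investigator withdraw a child for an adverse event or a newly met exclusion criterion. Recurrence is both (Sections 8.2.3 and 5.2). Absence from the count may therefore be related to the outcome and may differ by arm.

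Section 9.3.3 describes this check as a way to ensure that the design may prevent early recurrence before a larger trial. A signal missed because a few children were not counted would weaken that check.

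**Working it through.** **Plan's own figures.** The plan gives no dropout rate, no 90-day recurrence rate and no operating characteristics for the rule. Its only powered figure is for the future trial (Section 9.1: 30% recurrence, a 20-point difference, 80% power, 5% type 1 error). Taking 30% v 10%, two-sided, it reproduces:

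n = [1.96√(2×0.2×0.8) + 0.8416√(0.3×0.7 + 0.1×0.9)]² / 0.2² = (1.1087 + 0.4610)² / 0.04 = 61.6, so 62 per arm. This point does not affect it.

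**Inputs from the documents.** About 10 children per arm (Section 9.1); the rule fires when DB recurrences minus SB recurrences is at least 3 (Section 9.3.3).

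**Assumed inputs.** Recurrence risk over 90 days: SB stayers 10%, DB stayers 30%, leavers 60%. None has a source in the documents.

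**Formula.** With D and S the counts in the two arms, P(fires) = Σ P(S = s) × P(D ≥ s + 3). With 10 SB children at 10%, P(S = 0, 1, 2, 3, 4) = 0.3487, 0.3874, 0.1937, 0.0574, 0.0112.

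*Two DB leavers, not replaced, absent from the count* (8 DB children at 30%): P(D ≥ 3, 4, 5, 6, 7) = 0.4482, 0.1941, 0.0580, 0.0113, 0.0013.
P(fires) = 0.1563 + 0.0752 + 0.0112 + 0.0006 + 0.0000 = 0.243.

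*Same children, outcomes known* (8 at 30% plus 2 at 60%): P(D ≥ 3, 4, 5, 6, 7) = 0.7684, 0.5143, 0.2638, 0.0995, 0.0265.
P(fires) = 0.2679 + 0.1992 + 0.0511 + 0.0057 + 0.0003 = 0.524.

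The same formula gives the other cases:

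| Case | Leavers absent | Outcomes known |
|---|---|---|
| 1 DB leaver, not replaced | 0.313 | 0.453 |
| 2 DB leavers, not replaced | 0.243 | 0.524 |
| 3 DB leavers, not replaced | 0.178 | 0.594 |
| 2 DB leavers, replaced by children at 30% | 0.383 | 0.524 (the 10 first randomised) |
| 2 leavers at 60% in each arm, not replaced | 0.276 | 0.310 |
| 2 DB leavers, not replaced; stayers 20%, leavers 50% | 0.095 | 0.287 |
| 2 DB leavers at the stayers' 30%, not replaced | 0.243 | 0.383 |
| 2 DB leavers at the stayers' 30%, replaced | 0.383 | 0.383 |

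Three things follow. Replacement restores the number of children but not the leavers' outcomes, so the gap narrows from 24% v 52% to 38% v 52%. If leavers have the same risk as stayers, replacement removes the gap. If both arms lose similar children, the gap nearly closes.

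**Best and worst cases.** With u unknown children in the DB arm and v in the SB arm, the true DB minus SB difference lies between (observed − v) and (observed + u). With u = v = 2 and an observed difference of 1, the range is −1 to 3, which reaches the trigger.

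**The case against.** **The plan does not forbid a look-up.** True. Section 8.2.3 already sends events during the study to the chart and to REDCap under the Registry protocol. Neither that protocol nor the consent text is among the documents, so retrieval may already be permitted. What remains is that no rule is stated in advance, in a study whose investigators invented the device (Section 10.1.6).

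**Loss is already limited.** Stopping a bar does not end follow-up (Section 7.1), non-adherence and breakage do not cause withdrawal (Section 7.2), contact attempts are specified and visits are paid. This should keep the numbers small, but with a trigger of three, small numbers still count.

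**Unreplaced leavers have already been examined.** Those who leave after Visit 3 were due examinations at Days 0, 7 and 30, which cover the DB period; what is missing is Days 30 to 90, when all children wear the SB. This stands, and it favours counting all randomised children: those examinations exist, and the safety population discards them.

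**Registry data may come late.** With routine review every 3 to 6 months, often counted from about Day 0, the next visit will often fall after Day 90. It is unblinded, and the criterion of a 5-degree loss since the preceding visit depends on visit spacing. This also stands, so Registry findings can supplement the blinded result but cannot replace it.

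**Stronger readings that the documents do not support.** A reader might infer that a lost child is scored as free of recurrence; in fact the safety population leaves the child out. A reader might infer that leavers are the likeliest to recur; the 5- to 17-fold figure in Section 2.2 concerns intolerance and non-adherence, and nothing shows that lost children are those children. A reader might infer that a Registry look-up alone would correct the count; it would change nothing while the safety population is used.

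**Conclusion.** The point holds as a gap in the population and in outcome capture taken together. Children who leave are absent from the recurrence count, and no outcome is sought for them, although compulsory Registry enrolment and routine testing would often allow one to be found.

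The size is not known. Under the assumed risks, two absent DB leavers lower the chance of triggering the rule from 52% to 24% if not replaced and to 38% if replaced. With two such leavers in each arm the figures are 28% and 31%. The large effect therefore needs loss that is both higher-risk and concentrated in the DB arm.

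The endpoint is secondary and descriptive, is stated not to prove safety or efficacy, and does not touch the primary feasibility endpoint. This is a cheap improvement, not a flaw that undermines the trial.

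**What to change.** 1. **Section 9.3.3:** count recurrence by arm in all randomised children, including those who were replaced and those who left. Give denominators, since replacement can make the arms unequal. Report the number per arm with unknown status, and best- and worst-case counts.
2. **Sections 7.2 and 7.3:** for any randomised child without a Visit 4 examination, whose parent has neither left the Registry nor asked for data removal, read recurrence status and examination date from the Registry or chart up to a fixed cut-off stated in advance.
3. **Presentation:** show blinded study-visit outcomes in one column and Registry or chart outcomes in a separate, labelled column. Note that the latter are unblinded, that a recurrence first seen after Day 90 cannot be dated to the 90-day window, and that the change-since-preceding-visit criterion depends on visit spacing.

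The cost is protocol and consent wording and a few chart look-ups, with no extra visit or procedure. The downside is that the added examinations are unblinded and may be late, and a child who leaves the clinic altogether will remain unknown.

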8 STUDY ASSESSMENTS AND PROCEDURES

8.1 ASSESSMENTS

The physical exam that will be performed at each study visit will be done according to standard care for clubfoot. The only physical assessments that are not part of standard clubfoot care is measuring the patients' tibia length to ensure appropriate fit of the DB, as well as measuring the patients' height and weight to explore any possible reasons for bar malfunction or breakage. The height and weight of each participant will be measured and recorded by the blinded outcome assessor, with or without help of the clinic nurse, who routinely collects this data at SickKids.

To quantify parent perception and feedback, three different surveys will be administered to the parents/caregiver at scheduled times throughout the trial. This includes a survey at Day 0, Day 30, and Day 90 of the study period. Surveys will be completed in-person at the time of clinic visits, or via email after the visit if there was insufficient time to collect the data.

The purpose of the first survey on Day 0 is to assess parental perception of the SB prior to the study period. For the experimental arm, the second survey will assess parental perception of the new DB immediately after 30 days of wear, and the third survey will assess parental impression of returning to the SB after use of the DB at Day 90. For the control arm, the Day 30 and 90 surveys will serve as a test-retest reliability measure from Day 0 to assess if any variation over time (due to change in foot shape, treatment, recurrence, or environment) can be detected.

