1.2 SCHEMA

1.3 SCHEDULE OF ACTIVITIES (SOA)

Procedures	Screening Day -30 to -1	Baseline, Visit 1 Day 0	Study Visit 2 Day 7+/- 3 days	Study Visit 3 Day 30 +/-7 days	Study Visit 4 Day 90 +/- 7 days
Chart Review for screening	Х				
Measure patients for appropriate size of SB and DB		Х			
Informed consent		Х			
Complete Consent Discussion Form		Х			
Randomization		Х			
Prescribe study intervention (new DB or original SB)		Х			
Launch/retrieve data from temperature sensor in boot		х		х	х
Physical exam		Х	Х	Х	Х
Adverse event review			Х	Х	Х
Administer surveys		Х		Х	Х
Video record patients in their prescribed bar				х	

Procedures	Screening Day -30 to -1	Baseline, Visit 1 Day 0	Study Visit 2 Day 7 +/- 3 days	Study Visit 3 Day 30 +/-7 days	Study Visit 4 Day 90 +/- 7 days
Distribute/collect brace wear log		Х		Х	Х
Document on study enrollment log	Х	Х	Х	Х	Х

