3 OBJECTIVES AND ENDPOINTS

OBJECTIVES	ENDPOINTS	JUSTIFICATION FOR ENDPOINTS	
Primary			
To evaluate the ease of recruiting and retaining	Recruitment rate, dropout rate, and related responses on	This informs on the potential barriers to recruitment and	
participants for a randomized- controlled effectiveness trial of a novel FAB bar.	the parent-reported survey.	scale clinical trial to evaluate the effectiveness of the DB.	
Secondary			
1) To compare parental perception of the child's comfort in the SB versus the DB for foot abduction bracing in Ponseti clubfoot treatment.	1) Patient comfort levels determined by parent- reported surveys with 5-point Likert scale responses completed at Day 0, Day 30, and Day 90 of the study period.	1) Child comfort in brace is critical to achieving full brace compliance. As our study subjects are aged 1-3 years and unable to complete surveys or communicate their experience, parent-proxy reported outcome measures are a validated method to use as an endpoint (13, 14).	
2) To compare patient tolerance of the SB to the DB as measured by parent self-reporting and by how many hours the brace is worn per day as recorded by temperature sensors placed in the boots.	2) Daily brace wear hours as measured by a parent self- reported log and by temperature sensors implanted inside the boots.	2) Brace non-compliance is the leading cause of clubfoot recurrence. Therefore, increasing brace tolerance decreases clubfoot recurrence and leads to improved clinical outcomes.	
3) To perform a preliminary assessment of the effectiveness of the DB at preventing clubfoot recurrence during the bracing phase when the brace is worn as prescribed for a 30-day trial period.	3) Presence of clubfoot recurrence defined as a Pirani score > 0.5 representing any new development of cavus, adduction and/or hindfoot varus, or a loss of passive ankle dorsiflexion (equinus) of < 10 degrees above neutral or a reduction of 5 or more degrees from the previous visit.	3) While there is no validated definition for clubfoot recurrence, our clinical endpoints are commonly used criteria in other clubfoot studies. Since this is a feasibility study with only 20 participants, safety and efficacy cannot be clinically proven but we want to ensure the design at least prevents early relapse during the night-time bracing phase before the DB is produced at-large.	

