4 STUDY DESIGN

4.1 OVERALL DESIGN

This is an assessor-blinded randomized controlled trial in which patients with well-corrected idiopathic clubfoot will be randomized to wear either their original SB (which is standard care for clubfoot treatment) or the new DB for 30 days. After 30 days, all participants will resume use of the SB and be monitored for an additional 60 days.

This study is a "feasibility trial" as it is assessing the feasibility of conducting a large-scale randomized controlled trial to evaluate the effectiveness of the DB. As such, feasibility will be determined by the ability to recruit patients within the goal study period and to retain participants.

On Day 0 of the study period, patients will be randomized and receive baseline clinical and questionnaire evaluations. A temperature sensor will be added in each participant's boots during the 90-day study period to objectively measure time of brace wear.

All patients will be evaluated after 7 days in their assigned bar to check for brace fit, any complications, and to perform required adjustments. This 7-day checkup is standard care for clubfoot treatment when patients receive the SB and FAB for the first time.

After 30 days, the patients wearing the DB will resume use of the SB. All patients will be seen at the end of the first 30 days and after 90 days to monitor for recurrence of the clubfoot deformity, complications of brace wearing, and parent-reported perception of their child's comfort with the FAB. Parents will also be asked to complete a self-reported brace wear log that will be collected on Day 30 and 90.

A minimum of 10 patients per arm will be recruited. Once there are 10 in each arm, recruitment will halt. It is hypothesized that patients using the DB will experience higher brace tolerance as measured by the temperature sensors, and higher comfort levels as reported by parents, without an increase in clubfoot deformity recurrence compared to the SB.

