6.3 MEASURES TO MINIMIZE BIAS: RANDOMIZATION AND BLINDING

Each patient will be assigned a unique study ID. Patients will be assigned to an arm by drawing lots. This will be done by preparing 20 opaque, sealed envelopes. 10 of these envelopes will contain the word "Experimental," and the remaining 10 will contain the word "Control." On Day 0 of the study period, each participant will choose an envelope at random, and be assigned to that arm. This technique will ensure that the ratio between patients in each arm is 1:1.

To minimize bias, the outcomes assessor, who is an advanced practice physiotherapist clubfoot provider, will be independent of the study and design teams and blinded, so they will not know which bar has been assigned to which patient.

To ensure that the outcomes assessor remains blinded, a member of the study team will check in the patient at the beginning of each visit, remind the patient and parent about the blinding, and ensure that the bar is removed and hidden from view before the outcome assessor enters the evaluation room.

Unblinding may occur for any participant who has experienced an adverse event, such as clubfoot recurrence, and must return to their original SB, if not already using it. Unblinding will occur for all participants if any severe adverse event occurs that is related to the use of the DB. For unblinding to occur, the outcomes assessor must notify a member of the study team, and any member of the study team may unblind the outcomes assessor.

All intentional and unintentional breaking of the blind will be documented in the study's enrollment log, along with the reason(s) for unblinding. Per protocol, the Data Safety Monitoring Board and Research Ethics Board will also be notified of any adverse events or unblinding.

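### Section 8.1 allows the Day 0 comfort survey to be completed by email after the visit, and no readable text puts it before the envelope draw, so the baseline rating can be given with the arm known

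*Combined protocol and SAP*

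**What the plan says.** Section 8.1 lists three parent surveys, at Day 0, Day 30 and Day 90, and gives a single rule for completing them: "Surveys will be completed in-person at the time of clinic visits, or via email after the visit if there was insufficient time". No survey is exempted, and no deadline is set for an emailed reply.

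The same section gives the purpose of each survey. For Day 0: "The purpose of the first survey on Day 0 is to assess parental perception of the SB prior to the study period". In the experimental arm the Day 30 survey rates the dynamic bar (DB), and "the third survey will assess parental impression of returning to the SB after use of the DB at Day 90". In the control arm, Day 30 and Day 90 are read against Day 0 as a test-retest check on the standard bar (SB).

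On timing, section 4.1 says "Three surveys will be administered to parents on Day 0, Day 30, and Day 90 of the study period", and the comfort endpoint in section 3 rests on "Likert scale responses completed at Day 0, Day 30, and Day 90 of the study period".

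On allocation, section 6.3 says "On Day 0 of the study period, each participant will choose an envelope at random, and be assigned to that arm". Section 4.1 describes the day in one sentence: "On Day 0 of the study period, patients will be randomized and receive baseline clinical and questionnaire evaluations". The schedule of activities (section 1.3) marks consent, randomization, prescription of the bar and the surveys all at Visit 1. Blinding in section 6.3 covers the outcomes assessor only.

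**The concern.** A baseline rating is most useful when it is given before the rater knows the allocation. Here the parent is the rater and is present when the envelope is chosen. A parent who has just learned that the child will, or will not, get the new bar may rate the current bar differently. The informal evaluation in section 2.2 suggests that parents can hold a preference: 6 of 7 favoured a brace with more freedom of movement.

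Three uses of the Day 0 rating are exposed:

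- **Within-patient comparison (section 4.2).** In the experimental arm, Day 0 is the only SB rating before DB use. The other SB rating, at Day 90, follows DB use.
- **Control-arm reference (section 8.1).** Day 0 is the point against which stability over time is judged.
- **Analysis populations (section 9.2).** The comfort and discomfort populations are defined partly by a parent survey about the original brace. If that is the Day 0 survey, membership could depend on an answer given after allocation. Section 9.3.3 uses these populations for adherence as well as comfort.

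Parents will inevitably know the arm at Day 30 and Day 90. At Day 0 this is avoidable.

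**Working it through.** The plan gives no figure on this point to reproduce. The check is of sequence, followed by a small calculation of scale.

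**Step 1. Which surveys may be emailed?** The sentence in section 8.1 directly follows the list of all three surveys and has no exception, so Day 0 is included.

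**Step 2. When is the arm known?** At the Day 0 visit, when the envelope is drawn (section 6.3) and the bar prescribed (section 1.3). Any reply sent after that visit comes after allocation.

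**Step 3. Is the survey placed before the draw?** The sections on surveys, Day 0, randomization and blinding (1.1, 1.3, 3, 4.1, 4.2, 5.4, 6.3, 8.1, 9.2, 9.3.2 and 9.3.3) contain no such statement. Section 4.1 names randomization before the questionnaire, and the schedule lists surveys below randomization and prescription. Neither is a stated order of procedures. The schema in section 1.2 is a figure that is not shown, so this step covers the readable text only.

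**Step 4. What the text permits.**

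| Day 0 survey completed | Excluded by the text? | Arm known? | DB worn (experimental arm)? |
|---|---|---|---|
| On site, before the draw | No | No | No |
| On site, after the draw | No | Yes | At most at fitting |
| By email, same day | No | Yes | Usually not yet, as wear is mainly at night |
| By email, later day | Not by 8.1; it fits the Day 0 wording of sections 3 and 4.1 poorly | Yes | Possibly |

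Three of the four sequences give a baseline rating with the arm known.

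**Step 5. Where is time likely to run short?** Counting marks in the schedule gives 10 procedures at Day 0, 7 at Day 30 and 6 at Day 90. Fitting the sensor into the current boot may also fall on Day 0 (section 6.4). The stated trigger for email, lack of time, is therefore most plausible at the visit where order matters most.

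**Step 6. Scale.** With n = 10 per arm (section 4.1), one survey is 1/10 = 10% of an arm's baseline ratings. If k late ratings each move by d points in the same direction, the arm's Day 0 mean moves by k × d / n. The documents give neither k nor d. Assuming d = 1 point on the 5-point scale:

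- k = 1: 1 × 1 / 10 = 0.1 points
- k = 3: 3 × 1 / 10 = 0.3 points

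One child placed in the other comfort/discomfort population is 1/20 = 5% of participants. These figures show the weight of one response in a small trial. They do not estimate bias.

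**The case against.** **A reader might infer that the plan contradicts itself.** It does not clearly do so. The stated purpose of the Day 0 survey can be read as naming the experience to be rated, not the moment of reply, and a same-day email still fits the Day 0 wording in sections 3 and 4.1. Only a reply on a later day strains that wording. The accurate verb is that the plan allows a post-allocation baseline.

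**A reader might infer that the plan puts the survey after the draw.** The word order in section 4.1 and the row order in the schedule do not establish that. An on-site survey before the draw is fully compatible with the text, and the schema that is not shown might give an order.

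**A reader might infer that baseline ratings will often follow DB wear.** Email is a fallback and wear at this stage is mainly at night, so meaningful exposure needs a delayed reply. That is possible only because no time limit is set.

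**The stakes are limited.** The primary endpoint concerns recruitment and retention. Comfort is secondary and summarised descriptively (section 9.3.1). Section 9.2 does not say which survey it means, and its history-of-intolerance component does not depend on survey timing. Section 5.2 already excludes children with a current significant complaint of brace intolerance.

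All of this stands and narrows the point. It does not remove it, because the email rule itself permits the weaker baseline. The stated safeguard, neutral wording of the surveys (section 4.2), does not address when they are answered.

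**Conclusion.** The point holds as a weakness in sequence that the plan permits. Followed as written, it can yield a baseline SB comfort rating given with the arm known and, after a delayed reply, following some DB wear. The affected items are the experimental arm's only SB rating before DB use, the control arm's test-retest reference and, only if section 9.2 means the Day 0 survey, membership of the comfort and discomfort populations.

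The size and direction of any bias are unknown, as is the number of surveys that would be emailed; the 0.1 to 0.3 point illustration rests wholly on assumed values. Recruitment, dropout and the direct between-arm comparison at Day 30 are unaffected. The documents do not support a claim that the comfort results will be biased. The conclusion rests on the readable text and would fall away in part if the schema puts the survey before the draw; the email rule would still need a Day 0 exception. The change is worth making because it is specific and nearly free.

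**What to change.** - **Section 4.1 or a footnote to the schedule:** state that the Day 0 survey is completed in REDCap after consent and before the envelope is opened, and that the draw waits until the survey is submitted. This also tells staff what to do when time is short.
- **Section 8.1:** limit the email option to the Day 30 and Day 90 surveys.
- **Section 9.2:** state that the survey part of the comfort/discomfort classification uses the Day 0 survey. The history-of-intolerance part stays as it is.
- **Record-keeping:** note the time of the draw and flag any Day 0 survey with a later REDCap time stamp. Keep the response. Separate subgroup displays with and without it are not needed for a descriptive endpoint in about 20 children.

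The cost is a few sentences and a slightly longer Day 0 visit. REDCap is already used for consent and surveys (sections 5.4 and 4.1), so no new system is needed and no data are discarded.
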